7.3. Bone Safety Analyses

For the Week 48 analysis, summaries of BMD-related analyses will be provided for the double-blind phase based on the Spine and Whole Body DXA Analysis Sets. Summaries of bone biomarker analyses will be provided for the double blind phase based on the Safety Analysis Set. P-values comparing the two treatment groups, if specified, will be only calculated up to Week 48. Whole Body BMD measurements will exclude the head.

7.3.1. Bone Mineral Density (BMD)

Cumulative incidence of at least a 4% decrease from baseline in BMD of spine and whole body will be summarized by treatment group and visit, and compared between treatment groups using 95% confidence intervals for the difference in proportions based on the exact Chan-Zhang method {[Chan 1999](#)}.

Percent change from baseline in BMD of spine and whole body will be summarized by treatment group and visit during the double-blind phase. Percent change from baseline will be compared at each visit up to Week 48 between the treatment groups using analysis of variance (ANOVA) with treatment as a fixed effect. In addition, BMD of spine and whole body at each visit and change from baseline will be summarized by treatment group during the double blind phase.

The number and percentage subjects with percent change from baseline in spine and whole body BMD will also be summarized categorically by treatment group and visit using the following categories: $\leq -6\%$, $> -6\%$ to $\leq -4\%$, $> -4\%$ to $\leq -2\%$, $> -2\%$ to $\leq 0\%$, $> 0\%$ to $\leq 2\%$, $> 2\%$ to $\leq 4\%$, $> 4\%$ to $\leq 6\%$, $> 6\%$, and Missing. The distribution difference in these categories between the two treatment groups will be compared up to Week 48 using the CMH test (row mean scores differ statistic) based on observed data.

Spine and whole body Z-scores (derived from BMD assessment obtained via DXA scan) and changes in Z-scores from baseline will be summarized by treatment group and visit during the double-blind phase. Spine and whole body BMD clinical status will also be summarized categorically, and by categorical shift from baseline by treatment group using the following Z-score categories: > -1 , -1 to -2 , < -2 , and Missing. The shift from baseline in Z-score categories will be compared between treatment groups up to Week 48 using a rank analysis of covariance (ANCOVA) adjusting for baseline status {[LaVange 2008](#)} based on observed data. For categorical endpoints, percentages will be reported based on the number of non-missing measurements.

Mean (95% CIs) of the observed values for percentage change from baseline in spine and whole body BMD will be plotted by treatment group and across visits during the double-blind phase. Supportive listings will be provided for spine and whole body bone mineral density measurements, and for the subjects with at least 4% decline in spine and whole body bone mineral density.

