8.4. Secondary Endpoints

For Week 48, secondary endpoints to be evaluated in all subjects include:

- proportion of subjects with normal ALT and normalization of ALT
- composite endpoint of proportion of subjects with HBV DNA < 400 copies/mL and normal ALT

- proportion of subjects with HBV DNA < 169 copies/mL (29 IU/mL)
- proportions of subjects with HBsAg loss and seroconversion
- sequence changes from baseline within the HBV polymerase for subjects who were viremic (HBV DNA \geq 400 copies/mL [69 IU/mL]) at Weeks 48, 96, 144, 192 or Early Discontinuation; including subjects with confirmed virologic breakthrough
- cumulative incidence of at least a 4% decrease from baseline in bone mineral density of lumbar spine
- percent change from baseline in bone mineral density of lumbar spine

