8.9.4. Analyses of Bone Mineral Density and Bone Biochemical Markers

Cumulative incidence of at least a 4% decrease from baseline in bone mineral density of lumbar spine will be summarized and compared between treatment groups using 95% confidence intervals for the difference in proportions.

The percent change from baseline in bone mineral density of lumbar spine will be summarized over time and compared between treatment groups using the Wilcoxon rank sum test.

Lumbar spine Z-scores (derived from BMD assessment obtained via DEXA scan) and lumbar spine changes in Z-scores from study baseline will be summarized (n, mean, standard deviation, median, Q1, Q3, minimum and maximum) by treatment group and study week.

BMD assessments for whole body (via DEXA scan) and serum bone biochemical markers will be summarized over time. Changes from study baseline in bone biochemical markers will be summarized by treatment group, where study baseline will be defined as the mean of the Screening and Baseline Visit values.

Correlations between renal parameters and measurements of bone minerals density will be explored including exploration of the potential relationship between renal phosphate threshold (TmP/GFR) and measurements of bone mineral density.

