3.1.6. DXA Analysis Set

3.1.6.1. Spine DXA Analysis Set

The Spine DXA Analysis Set will include all subjects who were randomized and had received at least 1 dose of study drug, and had nonmissing baseline spine bone mineral density (BMD) values. Subjects will be analyzed according to the treatment they actually received during the double-blind phase.

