3.1.6.2. Whole Body DXA Analysis Set

The Whole Body DXA Analysis Set will include all subjects who were randomized and had received at least 1 dose of study drug, and had nonmissing baseline whole body BMD values. Subjects will be analyzed according to the treatment they actually received during the double-blind phase.

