3.3. Strata and Covariates

Randomization was stratified by age (2 to <6 and 6 to <12 years at the time of enrollment) and geographical location of study site (North America/Europe, and Asia). For all stratified analyses, age at baseline (<6 and ≥ 6 years) and geographical location of study site (North America/Europe, and Asia) will be used. If the number of subjects in a particular stratum is too small, this stratum may be combined with other strata for analysis. If there are discrepancies in stratification factor values between the IWRS and the clinical database at screening or baseline, the values recorded in the clinical database at baseline (or screening, if baseline is missing) will be used for stratified analyses.

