6.4. Changes From Protocol-Specified Efficacy Analyses

The protocol specifies that the analysis of the primary efficacy endpoint will evaluate the difference between the TDF and placebo treatment groups using a two-sided Fisher's exact test. This has been modified to a CMH test, controlling for the age group at baseline and region, in order to account for the stratified randomization used in the study. The age group at baseline was specified as <6 vs. ≥6 years, compared to the randomization strata age group of 2 to <6 and 6 to <12 years, as some subjects were age 12 by baseline. This change was also made for the analyses of the secondary endpoints. The two-sided Fisher's exact test will still be performed as a secondary analysis of the primary endpoint.

The PP Analysis Set, Serologically Evaluable FAS for HBeAg Loss/Seroconversion, and Serologically Evaluable FAS for HBsAg Loss/Seroconversion, was not defined in the protocol, but was added in the SAP.

For HBV DNA analyses, the default will be to report measurements in IU/mL, which is the current clinically accepted way to describe this parameter, instead of copies/mL.

For ALT normalized and normal analyses, both the AASLD and central lab normal ranges will be used.

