7.11. Changes From Protocol-Specified Safety Analyses

Baseline for BMD assessments for spine and whole body (via DXA scan) and serum bone biochemical markers will be calculated only using the Baseline Visit value, instead of taking the mean of the Screening and Baseline Visit values.

Treatment-emergent AEs and lab abnormalities were defined as any AE or lab abnormality that began on or after the study drug start date and no later than the study drug stop date in the protocol for those who discontinued study drug. This has been updated in this SAP to any AE with onset date on or after the blinded study drug start date and no later than the minimum of the blinded study drug stop date + 3 days and the first dose date of open-label study drug, if applicable for the double-blind phase, and to any AE with onset date on or after the open-label study drug start date and no later than the minimum of the open-label study drug stop date + 3 days for the open-label phase. This change was made as labs performed 1-2 days after study drug stopped were being excluded causing the measurement for the timepoint to be missed, even though protocol specified visit windows allowed for labs to be performed in a short period after the study drug was stopped.

Percent change from baseline in bone mineral density of lumbar spine was compared between treatment groups using ANOVA with treatment as a fixed effect, instead of the Wilcoxon rank sum test, to be consistent with other studies.

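### The BMD percent-change comparison leaves out the age and region strata and baseline BMD, all already collected, and so may report a wider interval than necessary

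*SAP*

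**What the plan says.** - **Model.** SAP 7.3.1 compares percent change in spine and whole body BMD between arms "using analysis of variance (ANOVA) with treatment as a fixed effect". No covariate is named and no adjusted sensitivity analysis is planned.
- **Reason given.** Protocol 8.9.4 had lumbar spine percent change "compared between treatment groups using the Wilcoxon rank sum test". SAP 7.11 says the ANOVA is used "instead of the Wilcoxon rank sum test, to be consistent with other studies".
- **Design.** SAP 3.3 states that randomisation was stratified by age (2 to <6, 6 to <12) and region (North America/Europe, Asia). SAP 6.4 replaces Fisher's test by a stratified CMH test for the primary endpoint "in order to account for the stratified randomization used in the study", and makes the same change for the secondary endpoints.
- **Baseline data.** Subjects enter the spine set only if they "had nonmissing baseline spine bone mineral density (BMD) values" (SAP 3.1.6.1), and the whole body set only if they "had nonmissing baseline whole body BMD values" (SAP 3.1.6.2).
- **Status.** Protocol 8.4 lists "percent change from baseline in bone mineral density of lumbar spine" among the Week 48 secondary endpoints. SAP 3.5 puts only the primary and key secondary endpoints in the gatekeeping sequence.

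**The concern.** The reason in SAP 7.11 explains the move away from a rank test. It does not explain leaving out the stratification factors, which SAP 6.4 treats as a reason to change the efficacy tests. Baseline BMD is also unused, although it is complete by definition of the analysis sets. Protocol 1.3.2 itself turns to Z-scores to allow for age-related change in BMD, so age is a plausible predictor.

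Two separate effects follow if the covariates matter:

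- **Strata.** Stratified allocation already balances age and region, so the estimate is hardly affected. A treatment-only model still counts the between-stratum variation in its standard error, so the interval is too wide and the test conservative.
- **Baseline BMD.** It is not balanced by design, so adjusting for it makes the estimate itself more precise. Omitting it leaves the test size near 5%.

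Protocol 1.3 names bone metabolism among the reasons for a placebo comparator, and only 89 subjects were treated (SAP 1.3). For a safety comparison, a conservative test is less able to show harm.

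**Working it through.** **Plan figures.** The documents give no SD, power or precision target for BMD, so there is no plan figure to reproduce on this point. The one stated power, at least 85% for the primary endpoint (67 vs 33, 21% vs 1%, two-sided Fisher), does reproduce: exact enumeration gives 88.3%.

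**Inputs.** N = 89 treated (SAP 1.3), split 59:30 as an assumption from the 2:1 ratio. The variance share R² explained by the covariates is not in the documents; the range taken is 0 to 0.4. Stratum shares (15/35/15/35%) and permuted blocks of 3 are assumed.

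**Absolute scale.** The adolescent study GS-US-174-0115 reports whole body changes of 2.8% vs 5.4%, p = 0.013, in 106 subjects (Protocol 1.2.3.1.4), of whom 54 were on placebo (Protocol 8.11). That leaves 106 − 54 = 52 on active drug, and 46/52 = 88.5% matches the quoted response rate. If a t-type test was used on all subjects:

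- t(104) for p = 0.013 is 2.527
- SE = 2.6 / 2.527 = 1.029
- SD = 1.029 / √(1/52 + 1/54) = 5.29 points (5.1 to 5.5 allowing for rounding; 4.9 if only 90 were analysed)
- ANOVA half-width here = t(0.975, 87) × 5.29 × √(1/59 + 1/30) = 2.36 points
- standardised difference = 2.6 / 5.29 = 0.49 SD

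**Simulation.** There were 10,000 trials per setting. ANOVA has treatment only; ANCOVA has treatment, age group, region and baseline BMD. In this table the strata supply the R². Ratio is the ANCOVA half-width over the ANOVA half-width, and the last half-width column is 2.36 × ratio.

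| R² | ANOVA size | ANCOVA size | Ratio | ANCOVA half-width | ANOVA power at 0.49 SD | ANCOVA power |
|---|---|---|---|---|---|---|
| 0 | 5.4% | 5.4% | 1.007 | 2.38 | 57.3% | 56.7% |
| 0.1 | 4.1% | 5.1% | 0.955 | 2.25 | 57.8% | 61.4% |
| 0.2 | 2.8% | 4.9% | 0.900 | 2.12 | 58.0% | 66.5% |
| 0.4 | 1.2% | 4.8% | 0.780 | 1.84 | 59.5% | 78.8% |

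If only baseline BMD predicts change, the ratios are 0.955, 0.901 and 0.781 at R² = 0.1, 0.2 and 0.4, and ANOVA size is 4.7%, 4.7% and 5.2%.

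**Break-even.** 1 − 1/1.007² = 0.014, so adjustment pays once R² exceeds about 1.4%. A closed-form calculation that charges all three covariates as if left to chance puts this at 3 to 4%. The simulation is lower because the blocks nearly balance age and region.

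**Where the width comes from.** In a run with strata R² = 0.3 and baseline R² = 0.1, the true SD of the estimate was 1.009 (ANOVA) and 0.925 (ANCOVA), with mean half-widths 2.359 and 1.841. Half-width over true SD is 2.359/1.009 = 2.34 for ANOVA and 1.841/0.925 = 1.99 for ANCOVA. A correctly calibrated interval needs about 1.99, so much of the ANOVA's extra width is an overstated standard error.

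**Sensitivity.** Blocks of 6 or uneven strata change the ratios by less than 0.003. With 70 usable scans they are 1.009–1.011, 0.957–0.960, 0.903–0.904 and 0.782–0.783.

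**The case against.** The strongest reply is that nothing here is wrong. The ANOVA is valid, no less adjusted than the protocol's Wilcoxon test, and outside the gatekeeping sequence. The SAP also leaves its other continuous comparisons unadjusted (HBV DNA, ALT and HBsAg in 6.2.2, bone markers in 7.3.2, eGFR in 7.4.1), so the treatment-only ANOVA fits a pattern. SAP 7.3.1 already plans a rank ANCOVA on shifts in Z-score category that takes baseline status into account, and Z-scores are age-referenced. The plan asks for no CI on the between-arm mean difference. The SD used for scale comes from whole body BMD in adolescents at Week 72, whereas the listed endpoint is lumbar spine at ages 2 to <12.

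Most of this is true and limits the point to efficiency. It does not remove the possible gain. The Z-score shift test is a coarser, different endpoint and ignores region. Unadjusted tests elsewhere are not a reason to omit covariates here. The half-width ratios do not depend on the borrowed SD; only the figures in points and the power figures do.

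One technical reservation stands. The figures assume baseline BMD predicts change equally in both arms. With an assumed slope of 0 on placebo and 0.8 residual SDs on active drug, the true SD of the estimate was about 0.25 under both models, so nothing was gained. The ANCOVA interval was still about 10% narrower, with test size about 6.0%. In another unequal-slope case the ANCOVA estimate was the more precise (0.252 vs 0.269). In neither case was the adjusted estimate materially worse.

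**Conclusion.** The point holds as a low-cost improvement, not as an error. The planned comparison is valid, but it omits two stratification factors and a complete baseline measurement without a stated reason. With a common baseline slope, the adjusted interval runs from 0.7% wider (covariates explain nothing) to 10% narrower at R² = 0.2 and 22% narrower at R² = 0.4. If the strata are what predicts change, the planned test is also conservative, down to 1.2% at R² = 0.4. The ANOVA's own power does not fall; what is forgone is the possible gain.

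The size rests on an R² the documents do not give, and on the assumed arm split, stratum shares and block size. The adolescent SD sets a scale only and says nothing about R². The primary conclusion is untouched. The Z-score change summaries and the Z-score category test give a partial age-referenced view, but neither adjusts the percent-change comparison.

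**What to change.** In SAP 7.3.1, compare percent change in spine and whole body BMD at each visit up to Week 48 by ANCOVA with treatment, age group (<6, ≥6 years), region and baseline BMD of the site analysed. Report the adjusted difference with its 95% CI. Keep the treatment-only ANOVA as supportive, which also preserves comparability with other studies. Record the change and its reason in SAP 7.11 before unblinding.

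The cost is SAP wording and one model statement. No new data are needed and no subject is lost, because both DXA sets already require baseline BMD. If the covariates explain nothing, the interval is about 0.7% wider (about 1% with 70 scans). Because the equal-slope assumption is untested, a supportive look at whether the baseline slope differs by arm would be sensible.

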Study GS-US-174-0115 was a large (n = 106 subjects) placebo-controlled, international trial in adolescent patients (12 to < 18 years). Preliminary analysis of the data suggest the following: after 72 weeks of treatment, tenofovir showed significant virologic response benefits over placebo. At 72 weeks, more tenofovir DF-treated subjects achieved the primary efficacy endpoint (serum HBV DNA < 400 copies/mL (69 IU/mL) at the end of blinded treatment), compared with placebo-treated subjects (88.5% vs. 0%, p < 0.001). Tenofovir DF treatment was well tolerated and no patients met the primary safety endpoint of a 6% decrease in lumbar spine bone mineral density (BMD). As expected for an adolescent population, both arms experienced an overall increase in mean lumbar spine BMD. Both populations also experienced an overall increase in mean whole body BMD; however, the percent increase in whole body BMD in tenofovir-treated subjects was less than the percent increase in whole body BMD attained by placebo-treated subjects (2.8% [TDF] vs. 5.4% [Placebo], p = 0.013).

- 1.2.3.1.5. Study GS-US-174-0121: A Randomized, Double-Blind, Double-Dummy Study Evaluating the Antiviral Efficacy, Safety, and Tolerability of TDF Monotherapy versus FTC plus TDF Fixed-Dose Combination Therapy in Subjects with CHB who are Resistant to Lamivudine

Study GS-US-174-0121 is fully enrolled (N = 280). As of January, 2011, 266 (95%) enrolled patients remain on study. Reasons for early termination (n = 14) are investigator's discretion (3 patients), protocol violation (3 patients), safety or tolerability reasons (3 patients), lost to follow-up (2 patients), withdrew consent (2 patients), and failure to meet entrance criteria (1 patient). This is a 5-year study; after all subjects complete the 96 week study visit a 96-week analysis was performed in the first quarter of 2012 for an interim Clinical Study Report.

- 1.2.3.1.6. Study GS-US-174-0123: A Phase 4, open-label, single-arm 48-week study evaluating the antiviral efficacy, safety, and tolerability of TDF in HBV mono-infected Asian-American adults

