In Study 321, bone effects were similar to adult subjects. Under normal circumstances BMD increases rapidly in this age group. In this study, the mean rate of bone gain was less in the tenofovir DF-treated group compared to the placebo group. Six tenofovir DF treated subjects and one placebo treated subject had significant ($> 4\%$) lumbar spine BMD loss in 48 weeks. Among 28 subjects receiving 96 weeks of tenofovir DF, Z-scores declined by 0.341 for lumbar spine and -0.458 for total body. Skeletal growth (height) appeared to be unaffected. Markers of bone turnover in tenofovir DF-treated pediatric subjects 12 years of age and older suggest increased bone turnover, consistent with the effects observed in adults.

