1.3.2. Rationale for Bone Mineral Density Evaluations

Osteopenia and osteoporosis have been reported in both children and adults with HIV-1 infection. The pathophysiology associated with these findings is unclear and may be related to HIV infection, antiretroviral therapy, and/or associated co-morbidities. Preclinical data showed that high doses of tenofovir DF in animals are associated with significant effects in bone metabolism. As seen in Study 926, some HIV-1-infected children receiving salvage therapy with

tenofovir DF experienced decreases in bone mineral density (BMD) {[Hazra et al 2005](#)}, {[Gafni et al 2006](#)}. Many of the children in that study had abnormal BMD results at baseline, suggesting that other factors were related to the decrease in BMD. As seen in a preliminary analysis of Study 115, in which adolescents age 12 to 17 with chronic HBV were treated with tenofovir or placebo and followed with DEXA scans at baseline, 24, 48, and 72 weeks, tenofovir was associated with a statistically significant difference in the mean percent increase in whole body BMD (2.8% [TDF] vs. 5.4% [Placebo], $p = 0.013$). Using whole body BMD Z-scores to account for age specific changes, and when comparing average values, it appears that this difference is unlikely to be of clinical relevance. Individual adolescent subjects who experienced the largest decreases in Z-scores were in the tenofovir arm; however, the largest changes in Z-scores in the study did not reach a change of -1.0.

The current study was designed to evaluate, in a controlled fashion, changes from baseline in BMD in a pediatric population following 48 weeks of study drug treatment. Changes from baseline in BMD will be evaluated every 24 weeks through Week 96, then annually until each subject reaches Week 192 (approximately 4 years on study), or at the Early Study Drug Discontinuation Visit (if applicable).

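### The only planned between-arm test on BMD Z-score uses three coarse classes and has low power; continuous Z-score change should be compared instead

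*SAP*

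**What the plan says.** SAP 7.3.1 handles Z-scores in two ways. For the continuous measure, at spine and whole body, "changes in Z-scores from baseline will be summarized by treatment group and visit during the double-blind phase"; no comparison of the arms is named. For the categorical measure it uses the "Z-score categories: > -1 , -1 to -2 , < -2 , and Missing" and then states: "The shift from baseline in Z-score categories will be compared between treatment groups up to Week 48 using a rank analysis of covariance", adjusted for baseline status and based on observed data. Under SAP 7.3, between-arm p-values for bone appear only where specified.

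Protocol 8.9.4 plans no Z-score test. It says only that "lumbar spine changes in Z-scores from study baseline will be summarized".

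The same SAP section compares the arms on bone in three other ways, none using the Z-score:
- For percent change in spine and whole-body BMD: "Percent change from baseline will be compared at each visit up to Week 48 between the treatment groups using analysis of variance (ANOVA". Treatment is that model's only term.
- A CMH row-mean-score test covers eight percent-change classes, four of which are gains.
- The incidence of a decrease of at least 4% is compared by an exact 95% confidence interval for the difference.

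**The concern.** In children aged 2 to under 12 the expected course is bone gain, so a drug effect on bone may show as slower gain rather than loss. Protocol 1.3.2 turns to whole-body Z-scores for this reason when it interprets the adolescent hepatitis B study (Study 115), and it judges clinical relevance on them. It adds that "the largest changes in Z-scores in the study did not reach a change of -1.0".

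A test on three classes records a child only when a cut-point at -1 or -2 is crossed. A fall from 0 to -0.9 counts as no shift, while a fall from -0.95 to -1.05 counts as one. Only the middle class has a width, of one Z unit; the outer two are open-ended. If mean effects are a few tenths of a unit, most affected children stay where they were.

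Protocol 1.3 gives more robust evaluation of bone metabolism as one reason for the placebo control. The single prespecified Z-score p-value would nevertheless come from a method that discards most of the information in the Z-score. A non-significant result would then say little about a growth-adjusted effect.

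**Working it through.** **Plan's own figure.** The documents state no power for any bone analysis. Their one power figure is for HBV DNA: at least 85% with 67 versus 33 and response 21% versus 1%. Exact enumeration of the two-sided Fisher test gives 88.3%, so that figure holds, but it does not bear on bone.

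**Inputs from the documents**
- Sample size (SAP 1.3): 89 children treated. At 2:1, 89 × 2/3 ≈ 59 on TDF and 30 on placebo.
- Effect (Protocol 1.2.3.1.9, Study 321): "Z-scores declined by 0.341 for lumbar spine and -0.458 for total body", in 28 subjects over 96 weeks. The second figure is read as a fall of 0.458.
- Pro rata to 48 weeks: 0.341 × 48/96 = 0.17 and 0.458 × 48/96 = 0.23.

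**Inputs assumed, because the documents do not give them**
- Baseline Z normal with mean 0, -0.5 or -1 and SD 1.
- SD of Z change 0.3, 0.4 or 0.5.
- Placebo mean change 0.
- The scaled falls taken as between-arm differences.
- Two-sided 0.05 and no missing scans.

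**How many children cross a cut-point.** If every child fell by exactly 0.23, only those starting between -1 and -0.77, or between -2 and -1.77, would change class. For baseline mean -0.5 the share is [Φ(-0.27) - Φ(-0.5)] + [Φ(-1.27) - Φ(-1.5)] = 0.085 + 0.035 = 12%. For mean 0 it is 0.062 + 0.016 = 8%, and for mean -1 it is 0.091 + 0.062 = 15%.

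**Power on continuous change, closed form.** Power ≈ Φ(δ / [s√(1/59 + 1/30)] - 1.96), where √(1/59 + 1/30) = 0.224.
- s = 0.3: standard error 0.067. δ = 0.17 gives Φ(0.57) = 71%; δ = 0.23 gives Φ(1.46) = 93%.
- s = 0.4: standard error 0.090. δ = 0.17 gives Φ(-0.06) = 47%; δ = 0.23 gives Φ(0.60) = 73%.
- s = 0.5: standard error 0.112. δ = 0.17 gives Φ(-0.44) = 33%; δ = 0.23 gives Φ(0.09) = 54%.

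**Power of both tests, simulated.** This used 3,000 runs per cell at 60 versus 30. The class-shift test regresses ranks of the Week 48 class on ranks of the baseline class and applies a mean-score test to the residuals. The continuous test is a two-sample t test on Z change. Cells show class-shift / continuous power.

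| Baseline mean Z | SD of change | Difference 0.17 | Difference 0.23 |
|---|---|---|---|
| 0 | 0.3 | 10% / 70% | 15% / 93% |
| 0 | 0.4 | 9% / 47% | 13% / 72% |
| 0 | 0.5 | 9% / 33% | 13% / 53% |
| -0.5 | 0.3 | 17% / 71% | 27% / 93% |
| -0.5 | 0.4 | 14% / 47% | 22% / 72% |
| -0.5 | 0.5 | 10% / 32% | 18% / 54% |
| -1 | 0.3 | 21% / 70% | 37% / 93% |
| -1 | 0.4 | 17% / 47% | 29% / 72% |
| -1 | 0.5 | 15% / 33% | 23% / 53% |

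Both tests hold their false-positive rate at about 4-6%. At 59 versus 30, with ANCOVA in place of the t test, the ranges are roughly 9-35% and 31-92%. The continuous test has more power in every cell, from about 2.2 times (33/15) to 7 times (70/10).

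**The percent-change ANOVA, for comparison.** Study 115 reports whole-body gains of 2.8% versus 5.4% at 72 weeks, p = 0.013. The difference of 2.6 points with z = 2.48 gives a standard error of 1.05. Assuming 45-52 and 48-54 subjects per arm, the SD is 5.0-5.4 points. At 60 versus 30, power for the full 2.6 points is about 58-63%. Scaled to 48 weeks (2.6 × 48/72 = 1.73 points) it is about 30-47%, depending on whether the SD is scaled too.

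**The case against.** The strongest reply is that bone is not left to the Z-score test. The ANOVA compares continuous percent change at both sites at each visit to Week 48, and four of the eight CMH classes are gain classes that respond to slower accrual. Randomization is stratified by age, so expected growth should be broadly balanced. Study 115 showed its difference on this kind of measure. This stands, and it confines the point to the Z-score test. It does not make that test adequate: the ANOVA has no age or growth term, and on the figures above its power is only moderate.

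Second, the effect sizes are borrowed. The Study 321 falls are within-arm, over 96 weeks, in HIV-infected adolescents on background regimens, and no placebo Z-score change is given. Halving them assumes linearity. Baseline Z and the SD of change are assumed as well. All of this stands, so the percentages are illustrative. The ordering of the two tests is firmer, since it held in every cell. The protocol's account of Study 352 also mentions a modest fall in total-body Z-score on tenofovir DF against no change in the comparator, but gives no size.

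Third, the protocol plans Z-scores as descriptive only, so no protocol-specified test is missing, and readers could derive a difference from the reported means and SDs. That is true, but the derived comparison would be post hoc and the prespecified p-value would still come from the weaker method.

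A reader might also infer that the 4% decrease endpoint is blind to this effect, since no Study 115 patient met a 6% limit. The documents do not support that. In Study 321, six tenofovir DF subjects and one placebo subject lost more than 4% of spine BMD in 48 weeks.

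**Conclusion.** The point holds for the Z-score comparison alone. The only between-arm test on the growth-adjusted measure is a three-class shift test, and continuous change, already derived and tabulated, is not compared. Under the stated assumptions the planned test would miss a between-arm difference of 0.17-0.23 in roughly 65-91% of trials (100% minus 9-35%), and ANCOVA on continuous change in roughly 8-69% (100% minus 31-92%). Missing scans would lower both powers.

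Two stronger readings go too far. One is that slowed bone accrual would mostly escape the plan altogether; the percent-change ANOVA and CMH comparisons stand against that. The other treats the full 96-week falls as 48-week differences between arms, which the documents do not support. On those unscaled values the class-shift test would reach 64% (0.341) or 88% (0.458) power at the most favourable setting, mean baseline Z of -1 and SD of change 0.3.

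This is a cheap improvement to a safety analysis. It does not affect the primary or key secondary conclusions.

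**What to change.** In SAP 7.3.1, prespecify a between-arm comparison of continuous change from baseline in spine and whole-body BMD Z-score at Weeks 24 and 48. Use ANCOVA with treatment and baseline Z-score as terms, in the respective DXA Analysis Sets, and report the mean difference with its 95% CI. Name this as the Z-score comparison, and keep the class-shift table as descriptive.

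The cost is SAP wording and one extra model per site and visit (two sites × two visits = four models), with no new data. The downside is additional safety comparisons that are not adjusted for multiplicity. They should be labelled so and read mainly through the estimates and intervals. The gatekeeping in SAP 3.5 covers only the primary and key secondary endpoints and is unaffected.
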